6.3.2 Criteria for Premature Termination or Suspension of Investigational Sites

A study site may be terminated prematurely or suspended if the site (including the investigator) is found in significant violation of GCP, protocol, or contractual agreement, is unable to ensure adequate performance of the study, or as otherwise permitted by the contractual agreement.

6.3.3 Procedures for Premature Termination or Suspension of the Study or the Participation of Investigational Sites

In the event that the sponsor, an institutional review board (IRB)/independent ethics committee (IEC) or regulatory authority elects to terminate or suspend the study or the participation of an investigational site, a study-specific procedure for early termination or suspension will be provided by the sponsor; the procedure will be followed by applicable investigational sites during the course of termination or study suspension.

7.0 SELECTION AND DISCONTINUATION/WITHDRAWAL OF SUBJECTS

All entry criteria, including test results, need to be confirmed prior to randomization.

7.1 Inclusion Criteria

Subject eligibility is determined according to the following criteria:

- 1. The subject is treated with antihypertensive therapy and has a post-washout mean sitting clinic SBP ≥150 and ≤180 mm Hg on Day 1; or the subject has not received antihypertensive treatment within 28 days prior to Screening and has a mean sitting clinic SBP ≥150 and ≤180 mm Hg at the Screening Visit and on Day 1.
- 2. The subject is a man or woman aged 18 years or older.
- 3. In the opinion of the investigator, the subject is capable of understanding and complying with protocol requirements.
- 4. The subject or, when applicable, the subject's legally acceptable representative signs and dates a written, informed consent form and any required privacy authorization prior to the initiation of any study procedures.
- 5. A female subject of childbearing potential* who is sexually active with a nonsterilized* male partner agrees to use routinely adequate contraception* from signing of informed consent through 30 days after last study drug dose.

*Definitions and acceptable methods of contraception are provided in Section 9.1.9 Contraception and Pregnancy Avoidance Procedure and reporting responsibilities are defined in Section 9.1.10 Pregnancy.

- 6. The subject has clinical laboratory test results (clinical chemistry, hematology, and complete urinalysis) within the reference range for the testing laboratory or the investigator does not consider the results to be clinically significant.
- 7. The subject is willing to discontinue current antihypertensive medications on Day -21 or on Day -28 if the subject is on amlodipine or chlorthalidone.

7.2 Exclusion Criteria

Any subject who meets any of the following criteria will not qualify for entry into the study:

- 1. The subject has a mean, sitting clinic DBP greater than 110 mm Hg at Day 1 (after placebo run in).
- 2. The subject is non-compliant (less than 70% or greater than 130%) with study medication during placebo run-in period.
- 3. The subject has secondary hypertension of any etiology (eg, renovascular disease documented as the cause of hypertension, pheochromocytoma, Cushing's syndrome).

- 4. The subject has a history of myocardial infarction, heart failure, unstable angina, coronary artery bypass graft, percutaneous coronary intervention, hypertensive encephalopathy, cerebrovascular accident, or transient ischemic attack.
- 5. The subject has clinically significant cardiac conduction defects (eg, third-degree atrioventricular block, sick sinus syndrome).
- 6. The subject has hemodynamically significant left ventricular outflow obstruction due to aortic valvular disease and hypertrophic obstructive cardiomyopathy (HOCM).
- 7. The subject has severe renal dysfunction or disease (based on estimated glomerular filtration rate [GFR] <30 mL/min/1.73 m²) at Screening.
- 8. The subject has known or suspected unilateral or bilateral renal artery stenosis.
- 9. The subject has a history of cancer that has not been in remission for at least 5 years prior to the first dose of study drug. (This criterion does not apply to those subjects with basal cell or Stage 1 squamous cell carcinoma of the skin).
- 10. The subject has type 1 or poorly controlled type 2 diabetes mellitus (hemoglobin A1c [HbA1c] >8.5%) at Screening.
- 11. The subject has hyperkalemia (defined as serum potassium above the normal reference range of the central laboratory) at Screening.
- 12. The subject has an alanine aminotransferase (ALT) or aspartate aminotransferase (AST) level of greater than 2.5 times the upper limit of normal (ULN), active liver disease, or jaundice at Screening.
- 13. The subject has any other known serious disease or condition at Screening (or Randomization) that would compromise subject safety, might affect life expectancy, or make it difficult to successfully manage and follow the subject according to the protocol.
- 14. The subject has a history of hypersensitivity or allergies to TAK-491 (azilsartan medoxomil), any of its excipients or other angiotension II (AII) receptor blockers (ARBs).
- 15. If female, the subject is pregnant or lactating or intending to become pregnant before, during, or within 30 days after participating in this study; or intending to donate ova during such time period.
- 16. The subject currently is participating in another investigational study or is receiving or has received any investigational compound within 30 days prior to the first dose of study medication
 - Note: This criterion does not apply to subjects who participated in observational studies that lacked an intervention or invasive procedure.
- 17. The subject is an immediate family member, study site employee, or is in a dependant relationship with a study site employee who is involved in conduct of this study (eg, spouse, parent, child, sibling) or may consent under duress.

- 18. The subject has a history of drug abuse (defined as any illicit drug use) or a history of alcohol abuse within the past 2 years.
- 19. The subject is taking or expected to take an excluded medication listed in Section 7.3 of the protocol.
- 20. The subject works a night (third) shift (defined as 11 PM [2300] to 7 AM [0700]). (Only for subjects with ABPM)
- 21. The subject has an upper arm circumference <24 cm or >42 cm. (Only for subjects with ABPM)

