- A female subject of childbearing potential who is sexually active with a nonsterilized male partner agrees to use routinely adequate contraception from signing of informed consent through 30 days after last study drug dose.
- The subject has clinical laboratory test results (clinical chemistry, hematology, and complete urinalysis) within the reference range for the testing laboratory or the investigator does not consider the results to be clinically significant.
- The subject is willing to discontinue current antihypertensive medications on Day -21 or on Day -28 if the subject is on amlodipine or chlorthalidone.

Main Criteria for Exclusion:

- The subject has a mean sitting, clinic diastolic blood pressure (DBP) greater than 110 mm Hg at Day 1(after placebo run in).
- The subject is non-compliant (less than 70% or greater than 130%) with study medication during placebo run-in period.
- The subject has secondary hypertension of any etiology (eg, renovascular disease documented as the cause of hypertension, pheochromocytoma, Cushing's syndrome).
- The subject has a history of myocardial infarction, heart failure, unstable angina, coronary artery bypass graft, percutaneous coronary intervention, hypertensive encephalopathy, cerebrovascular accident, or transient ischemic attack.
- The subject has clinically significant cardiac conduction defects (eg, third-degree atrioventricular block, sick sinus syndrome).
- The subject has hemodynamically significant left ventricular outflow obstruction due to aortic valvular disease or hypertrophic obstructive cardiomyopathy.
- The subject has severe renal dysfunction or disease (based on estimated glomerular filtration rate <30 mL/min/1.73 m²) at Screening.
- Subject has known or suspected unilateral or bilateral renal artery stenosis.
- The subject has a history of cancer that has not been in remission for at least 5 years prior to the first dose of study drug. (This criterion does not apply to those subjects with basal cell or Stage 1 squamous cell carcinoma of the skin).
- The subject has type 1 or poorly controlled type 2 diabetes mellitus (hemoglobin A1c [HbA1c] >8.5%) at Screening.
- The subject has hyperkalemia (defined as serum potassium above the normal reference range of the central laboratory) at Screening.
- The subject has an alanine aminotransferase (ALT) or aspartate aminotransferase (AST) level of greater than 2.5 times the upper limit of normal (ULN), active liver disease, or jaundice at Screening.

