4.3 Summary of Clinical Data

After oral administration, TAK-491 is converted to the active moiety TAK-536 by ester hydrolysis in the gut and/or during the process of absorption. Conversion is rapid, as the salt free form of TAK-491 (TAK-491F) is undetectable in human plasma at the earliest time points examined (5 minutes following administration of single oral doses of TAK-491 at 40 and 80 mg and 15 minutes following multiple oral doses of TAK-491 at 320 mg). TAK-536 undergoes extensive metabolism to TAK-536 M-I and TAK-536 M-II. Following both single and multiple dosing of TAK-491 tablets, dose proportionality was established for TAK-536 and TAK-536 M-II area under the plasma concentration-time curve and maximum observed plasma concentration values over the dose range of 20 to 320 mg.

TAK-491 has been evaluated in 17 phase 1 studies and 1 phase 2 study. The phase 3 program consisted of 5 randomized, controlled, monotherapy studies of 6 weeks or 6 months duration; 2 randomized, controlled, 6-week studies in which TAK-491 was coadministered with the thiazide-like diuretic chlorthalidone or the calcium channel blocker (CCB) amlodipine; and 2 open-label studies of up to 56 weeks duration.

Dose adjustment is not needed based on age, gender, or race.

Steady-state total exposures to TAK-536 after multiple doses of TAK-491 in a phase 1 hepatic impairment study were approximately 28% and 64% greater in subjects with mild and moderate hepatic impairment, respectively, than in healthy subjects. Subjects with severe hepatic impairment were not studied. The increases in exposure to TAK-536 in the phase 1 hepatic impairment study are not considered to be clinically meaningful as TAK-491 was well-tolerated in other pharmacokinetic studies in which exposures to TAK-536 were greater than those observed in subjects with hepatic impairment. Therefore, TAK-491 dose reduction is not necessary for subjects with mild or moderate hepatic impairment, although subjects with any degree of hepatic impairment are excluded from the present study.

The single dose phase 1 study in renal impaired subjects showed that after 40 mg TAK-491 dosing, total exposure to TAK-536 tended to be higher in subjects with renal impairment than in healthy subjects with increases of 30%, 25%, 95%, and 4% in subjects with mild, moderate, or severe renal

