9.1.13 Documentation of Randomization and Run-In Failure

Only subjects who meet all of the inclusion criteria and none of the exclusion criteria are eligible for randomization into the treatment phase. The IVRS/IWRS will be contacted for treatment assignment and this information should be captured on the appropriate (e)CRFs.

If the subject is found to be not eligible for randomization, the investigator should record the primary reason for failure on the applicable (e)CRF. If the subject has begun the single-blind placebo run-in study medication and they are found to not be eligible for randomization, they are considered a run-in failure. The investigator or designee should complete the appropriate (e)CRFs and register the subject as a run-in failure in the IVRS/IWRS.

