14.2 Protocol Deviations

The investigator should not deviate from the protocol, except where necessary to eliminate an immediate hazard to study subjects. Should other unexpected circumstances arise that will require deviation from protocol-specified procedures, the investigator should consult with the medical monitor (and IRB or IEC, as required) to determine the appropriate course of action. There will be no exemptions (a prospective approved deviation) from the inclusion or exclusion criteria.

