Page 15, Study Summary: Statistical Considerations, Analysis Sets

Existing Text

Safety Analysis Set: All subjects who receive at least 1 dose of double-blind study medication. Subjects will be analyzed according to the study medication they received.

Full Analysis Set (FAS): All randomized subjects who received at least 1 dose of study medication. Subjects will be analyzed according to the treatment group to which they were randomized.

Revised Text

Safety Analysis Set: All subjects who receive at least 1 dose of double-blind study medication. Subjects will be analyzed according to the study medication they received.

Full Analysis Set (FAS): All randomized subjects who received at least 1 dose of study medication. Subjects will be analyzed according to the treatment group to which they were randomized

Subjects who were randomized more than once will be excluded from both the safety analysis set and the FAS.

Rational for Amendment

For clarity.

Page 21, Section 4.3: Summary of Clinical Data (paragraph 4)

Existing Text

TAK-491 dose reduction is not necessary for subjects with mild or moderate hepatic impairment, although such subjects are excluded from the present study.

Revised Text

Steady-state total exposures to TAK-536 after multiple doses of TAK-491 in a phase 1 hepatic impairment study were approximately 28% and 64% greater in subjects with mild and moderate hepatic impairment, respectively, than in healthy subjects. Subjects with severe hepatic impairment were not studied. The increases in exposure to TAK-536 in the phase 1 hepatic impairment study are not considered to be clinically meaningful as TAK-491 was well-tolerated in other pharmacokinetic studies in which exposures to TAK-536 were greater than those observed in subjects with hepatic impairment. Therefore, TAK-491 dose reduction is not necessary for subjects with mild or moderate hepatic impairment, although subjects with any degree of hepatic impairment are excluded from the present study.

Rational for Amendment

To add clinical data from the phase 1 hepatic impairment study to support the addition of Week 2 clinical laboratory tests.

Page 21, Section 4.3: Summary of Clinical Data (paragraph 5)

Existing Text

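### Exclusion 6 in Section 7.2 joins two causes of left ventricular outflow obstruction with *and* where the synopsis has *or*; read literally, a patient with only one cause is not excluded

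*Protocol*

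**What the plan says.** The criterion appears twice in the protocol.

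- Section 7.2, exclusion 6: "hemodynamically significant left ventricular outflow obstruction due to aortic valvular disease and hypertrophic obstructive cardiomyopathy (HOCM".
- Section 2.0, Main Criteria for Exclusion: "hemodynamically significant left ventricular outflow obstruction due to aortic valvular disease or hypertrophic obstructive cardiomyopathy".

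Three other provisions make the wording of the Section 7 list matter. Section 7.0 says: "All entry criteria, including test results, need to be confirmed prior to randomization". Section 9.1.13 says: "Only subjects who meet all of the inclusion criteria and none of the exclusion criteria are eligible for randomization into the treatment phase". Section 14.2 says: "There will be no exemptions (a prospective approved deviation) from the inclusion or exclusion criteria". Section 9.3.1 directs screening to the criteria in Section 7.0, not to the synopsis.

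Exclusion 13 in Section 7.2 is a general clause. It covers any other known serious disease that would compromise the subject's safety, might affect life expectancy, or would make the subject hard to manage and follow under the protocol.

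The SAP does not restate the exclusion list.

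**The concern.** One criterion has two wordings in the same protocol, and they do not mean the same thing when read literally. The narrower one stands in the list that sites apply at screening and randomization. The protocol gives no reason for exclusion 6, but it sits among the cardiac exclusions, and I take it to be there for patient safety.

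Two things are at stake. First, a patient with significant obstruction from a single cause could pass exclusion 6 at a site that reads the text strictly. Second, the same patient, once randomized, would be an eligibility deviation on the synopsis wording but not on the literal Section 7.2 wording. With exemptions barred and about 20 to 25 sites making these decisions, the list should have one reading.

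**Working it through.** No arithmetic applies; this is a comparison of texts.

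1. **Status of the two texts.** Both come from the current protocol body and synopsis. Neither is superseded text from the amendment log, and neither passage shows sign of redaction or broken extraction.

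2. **What differs.** The condition (hemodynamically significant left ventricular outflow obstruction) and the two named causes are the same. Apart from the abbreviation added in Section 7.2, the only difference is the conjunction.

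3. **What each excludes, read literally.** Under the synopsis, obstruction from either cause excludes. Under Section 7.2, the obstruction must be due to both. A patient with obstruction from aortic valve disease alone is excluded by the synopsis and not by the literal Section 7.2 text. The same holds for a patient with HOCM alone.

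4. **Which text governs.** I found no rule of precedence between synopsis and body. Section 9.3.1 sends the site to Section 7.0 for the entry criteria, so Section 7.2 is the operative list.

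5. **Whether another criterion closes the gap.** Exclusion 4 lists past cardiac and cerebrovascular events and procedures, including heart failure, but not outflow obstruction. Exclusion 5 concerns conduction defects. Exclusion 13 can apply, but only if the investigator judges the condition serious enough. It therefore replaces a definite exclusion with a judgement.

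6. **Whether the analysis is touched.** The full analysis set is defined by randomization and dosing (SAP Section 7.3). The listed per-protocol exclusions concern Day 1 systolic pressure, treatment received, repeat randomization, deviations affecting baseline blood pressure, compliance and prohibited medication. None turns on exclusion 6 as such. The sample size, margin and ANCOVA model do not depend on it.

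**The case against.** The best reply is that this is an editorial slip with a natural benign reading. A phrase of the form *due to A and B* is often just a list of causes. The strict reading gives an odd criterion that nobody would have designed, and the synopsis shows the intent. The obstruction must also be hemodynamically significant, so it is hard to picture an investigator who would not regard it as a serious condition under exclusion 13. To be randomized, such a patient would need an investigator who took the strict reading, overlooked the synopsis and judged exclusion 13 not met.

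Most of that stands, and it is why the point is minor. It does not remove the discrepancy: the operative list still says something different from the synopsis, and a safety exclusion should not need to be rescued by a judgement clause.

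A reader might also infer a second gap, for hepatic impairment. Section 4.3 ends its hepatic paragraph with "although subjects with any degree of hepatic impairment are excluded from the present study", while exclusion 12 excludes an ALT or AST "level of greater than 2.5 times the upper limit of normal (ULN), active liver disease, or jaundice at Screening" and does not name hepatic impairment. The documents do not support treating this as a gap in the entry criteria:

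- Section 4.3 is a background summary, not an eligibility section, and its sentence can be read as shorthand for exclusion 12.
- Active liver disease, in exclusion 12, is an open clinical term with no threshold and can cover much hepatic impairment.
- Inclusion 6 requires screening laboratory results, which include albumin, bilirubin, alkaline phosphatase and GGT, to be in range or judged not clinically significant.
- Section 4.3 itself describes the exposure increases in mild and moderate impairment as not clinically meaningful.

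What remains is that the background sentence is worded more broadly than the criterion.

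**Conclusion.** The discrepancy in exclusion 6 is real. Read literally, the operative list fails to exclude a patient with hemodynamically significant outflow obstruction from one cause alone and leaves that patient to exclusion 13. This is a minor correction to a safety criterion.

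The conclusion rests on two assumptions: that Section 7.2 is what sites apply, which Section 9.3.1 supports, and that the synopsis states the intended rule, which is by far the more sensible reading. The number of patients affected cannot be derived from the documents.

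A reader might go further and infer that such patients were enrolled, that harm followed, or that the sponsor chose to narrow the criterion. Nothing in the documents supports any of these. Endpoint, power, error control and the primary analysis are unaffected.

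**What to change.** In Section 7.2, exclusion 6, change *and* to *or* so that it matches the synopsis. The cost is one word in the next amendment. It needs no new procedure and no new data, and it leaves the SAP unchanged. Until then, a short clarification to sites that either cause excludes would serve.

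Optional editorial note: the Section 4.3 sentence on hepatic impairment could be reworded to describe what exclusion 12 excludes. That would change nobody's eligibility.

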7.3 Excluded Medications and Treatments

- Antihypertensive agents, including those used for treatment of other conditions, such as benign prostatic hyperplasia (α-blockers) or edema (diuretics). Those used at screening must be discontinued for the washout/run-in period through the completion of final in-clinic procedures at Week 8/Early Termination (Visit 9). Amlodipine and chlorthalidone should be discontinued on Day -28, while all other antihypertensive medications should be discontinued on Day -21. If necessary, medications that need to be stopped gradually may be tapered in the first week of screening, but must be discontinued completely by Day -14.
- Other agents that alter BP are excluded from the beginning of the run-in period through the remainder of the study. These include:
 - Tricyclic antidepressants.
 - Monoamine oxidase (MAO) inhibitors.
 - Central nervous system stimulants.
 - Amphetamines or their derivatives.
 - Dopamine agonists.
 - Atypical antipsychotic agents.
 - Trazodone.
 - Lithium.
 - Diet medications (except orlistat).
 - Nitrates.
 - Thiazolidinediones.
- Conditionally excluded medications as specified:
 - Phosphodiesterase type 5 (PDE5) inhibitors within 72 hours of a clinic visit.

- Chronically used (defined as more than 3 doses per week) common cold medications with pseudoephedrine or phenylephrine, or nonsteroidal anti-inflammatory drugs (NSAIDs), including aspirin >325 mg/day or cyclooxygenase-2 (COX-2) inhibitors.
- Systemic use of corticosteroids (topical or inhaled is acceptable).
- Subjects will be instructed not to take any medications, including over-the-counter products, without first consulting the investigator.

7.4 Diet, Fluid, Activity Control

Subjects should be encouraged to avoid foods high in sodium and avoid adding extra salt to food since excessive sodium consumption may elevate blood pressure in certain individuals. Otherwise, subjects should maintain their usual diet prior to, and during the study.

For a subject with signs of volume depletion, such as weight loss or orthostatic hypotension (BP decreases by ≥ 20 mm Hg systolic or ≥ 10 mm Hg diastolic after standing for 2 minutes), inquire about other sources of volume loss (eg, diarrhea, vomiting, poor oral intake). If there is evidence of volume depletion, consider temporarily liberalizing salt intake and encouraging increased hydration. If these measures do not alleviate the orthostatic hypotension, the case should be discussed with the medical monitor and the subject considered for withdrawal.

After informed consent is provided, subjects will be asked to fast prior to blood draws within the Screening Period, and will be instructed to fast for at least 8 hours prior to returning to the study site for Day 1 (Visit 5), Week 2 (Visit 6), Week 4 (Visit 7), and Week 8/ET (Visit 9).

